- Spatial Navigation Task (version B) - delay phase - 10 minutes. Following a 30-minute delay (during which the task-switching and associative learning tasks are completed), participants will be asked to re-trace their route to a given landmark.
- Processing speed measures (Digit symbol substitution, pattern comparison, letter comparison)

13. Randomization

Randomization will occur once to determine the order of exercise conditions for the acute cross-over design, and again to determine the training groups (see Figure 1). Eligible participants will be randomized to one of two randomization groups that indicates the order of their acute exercise conditions, a separate randomization will occur to determine their exercise training group (see

Figure 1). Therefore, *all* enrolled participants complete an acute exercise assessment with both light and moderate intensity sessions (21). Following the acute exercise session, participants will continue in one of two training groups (moderate, light intensity).

When participants express interest to participate in their exercises as a couple (dyad), co-enrollment will be allowed on a limited basis. Co-enrollment means that only one of the dyad will be randomized and the partner will be automatically assigned to the same intervention group. The data for the partner then qualifies as “missing” for all analyses that depend on assumptions of random assignment. Our power analysis accounted for losing up to 15% of data due to drop out (10%) and scanner motion (5%), which would leave the sample at about 100 participants and still at strong power (~90%, two-tailed) with allowance for covariates. Based on our pilot study and adherence so far, we predict to lose less data from drop-out and motion than we initially predicted. Therefore, we will consider non-randomized partners as another source of “missing data” and set our limit for non-randomized dyads to N=6 (5%).

For participants who drop-out after randomization, we will take the following approach to determine the best type of post-testing to be done at the time of drop-out:

- First, ask them if they are still willing to do their post-test MRI and full cognitive testing sessions.
- If they cannot do all the testing, we will ask if they could do one 2-hour cognitive testing session in the lab. This would allow us to collect our learning and memory behavioral measures that tap into hippocampal function and our abbreviated battery including the RAVLT in-person.

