- However, if the drop-out participant is not willing to return to the lab for post-testing, then we will ask them if they are willing to do a brief phone survey which includes the tasks in the short battery above.

14. Neuroimaging measures

This study will utilize the 3T GE Discovery 750W MRI scanner to collect images that allow us to measure brain structure (T1, T2, diffusion), functional connectivity of brain networks sensitive to aging (resting state BOLD), neuronal metabolism (quantitative susceptibility mapping and T1ρ), and cerebrovascular reactivity (BOLD response during a breath hold paradigm). We expect to scan for one hour before each acute exercise session and 30 minutes following each acute exercise session, and for 1 hour following completion of the 6-month exercise training intervention (see outline below). In the event that a participant is uncomfortable in the scanner (e.g., wide shoulders or large head size), but would like to participate in scanning, we will prioritize T1 structural images and resting state fMRI scans which are central to testing our specific aims. Following each MRI session, images will be downloaded directly from XNAT into [BIDS](#) format. Quality control procedures will be conducted following data collection each week using [mriqc](#).

MRI scans acquired at first baseline MRI visit:

- Pre-exercise:
 - 3 x 8min resting state fMRI scans (eyes open)
 - Breath-hold task

- T1 weighted anatomical image (MPRAGE)
- T2 FLAIR anatomical image
- Post-exercise:
 - 3 x 8min resting state fMRI scans (eyes open)

MRI scans acquired at second baseline MRI visit:

- Pre-exercise:
 - 3 x 8min resting state fMRI scans (eyes open)
 - 64 Directional DTI scan to assess white matter integrity
 - T1 ρ
- Post-exercise:
 - 3 x 8min resting state fMRI scans (eyes open)

MRI scans acquired at post-training MRI visit:

- 3 x 8min resting state fMRI scans (eyes open)
- Breath-hold task
- T1 weighted anatomical image (MPRAGE)
- T2 FLAIR anatomical image
- 64 Directional DTI scan to assess white matter integrity
- T1 ρ

*Note the post-test MRI will begin in the mock MRI room with assessment of the RAVLT, oral trail-making, and the FAS word fluency tasks.

15. Research Interventions

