Computers will be used to store and analyze clinical data and we will address elements of computer security to ensure that the data remain confidential.

17. Overall Data Analysis Approach

The primary analysis concerns the difference in functional connectivity among the chronic treatment groups of moderate intensity (M) and light intensity (L) at the single terminus (last visit) of the 6-month RCT. Multiple regression will be used to regress functional connectivity (FC) on dummy coded group membership, and the stratification variables of age and sex.

Suppose that FC for the i^{th} participant at the end of the study is denoted as y_i ($i = 1, \dots, N$) and group is coded as $grp_i = 1$ if M and $grp_i = 0$ if L. Then the multiple regression model for the primary analysis is

$$y_i = \beta_0 + \beta_1 grp_i + \beta_2 sex_i + \beta_3 age_i + e_i.$$

Under the typical assumption that e_i is normally distributed, the coefficients can be estimated using ordinary least squares. The null hypothesis of interest is that there is no group difference, $H_0: \beta_1 = 0$, which can be evaluated with a t -test. In order to account for missing data, multiple imputation will be used, and the null hypothesis of interest will be evaluated based on pooled estimates using Rubin's rules (23). In order to ensure maximal statistical power for the primary aim, the first analysis will have a single outcome, which is the average FC between the posterior hippocampus, posterior cingulate cortex, and the ventral medial prefrontal cortex. Additional exploratory analysis will be performed on individual connections with adjustment for multiple testing (i.e., adjustment for false discovery rate within a region of interest).

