The interaction term allows the effect of the acute M – L difference to vary by chronic group. When $\gamma_3 \neq 0$, the acute difference has a different effect for the chronic M group. Therefore, the null hypothesis of interest for the second aim is $H_0: \gamma_3 = 0$. Missing data will again be handled with multiple imputation. The first test will consist of the same hippocampal-cortical outcome described above, and additional exploratory analysis will be performed adjusting for multiple testing.

The main analysis for all three aims will be conducted under the intent-to-treat (ITT) principle. A participant will be counted as a member of their group at the time of re-randomization in the chronic phase. Participants will be analyzed in their initial group assignments in a blinded manner, regardless of dropout or adherence. Fidelity will be assessed by separate regression models in which CRF is the outcome with the goal of examining if the treatment caused a sufficient difference in CRF. A small number of participants will be allowed to enroll as a couple with the couple being the unit for random assignment. One member of the couple will be randomly assigned for analysis and the other member's data will not be considered for analysis in the primary aim (data might be inspected for exploratory purposes).

Due to its importance in achieving our objectives, the power analysis is based on preliminary data for the relationship between aerobic exercise training change in learning rate on one of the learning tasks. Based on the effect size observed from a multiple linear regression of training group and additional covariates as predictors, our power analysis maintains an allowance of 10 predictor variables including training group. Based on these considerations, a sample size of 120 older adults, randomized to one of two training groups (N=60 per group), would ensure 95% power. If we further account for up to ~15% (N=18) missing data due to factors such as (a) motion or drop-out during scanning, (b) missing post-test due to drop-out during training, or (c) co-enrollment with spouse, we would still have a final sample size of ~N=100, which would achieve ~90% two-tailed power and still result in larger group sizes than our published results of hippocampal-cortical FC following exercise training. We do not have plans for formal interim analyses and there is no predefined interim statistical analysis or result that would cause termination of the trial.

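### Drop-outs are never offered the post-test MRI without the full cognitive set, so the primary outcome can be lost in people who would have accepted a scan

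*Protocol*

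**What the plan says.** Protocol section 13 lists three offers, in order, for a participant who drops out after randomization:

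1. "First, ask them if they are still willing to do their post-test MRI and full cognitive testing sessions".
2. "If they cannot do all the testing, we will ask if they could do one 2-hour cognitive testing session in the lab". The reason given is: "This would allow us to collect our learning and memory behavioral measures that tap into hippocampal function", together with an abbreviated battery that includes the RAVLT.
3. For those who will not return to the lab, "we will ask them if they are willing to do a brief phone survey".

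The section describes this as post-testing done when the participant drops out.

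Protocol section 17 and SAP section 17 define what the trial needs from that visit. "The primary analysis concerns the difference in functional connectivity among the chronic treatment groups" at the last visit of the 6-month trial, and "the first analysis will have a single outcome, which is the average FC between the posterior hippocampus", posterior cingulate and ventromedial prefrontal cortex. On the analysis set: "Participants will be analyzed in their initial group assignments in a blinded manner, regardless of dropout or adherence". Missing values are multiply imputed, with a pattern-mixture sensitivity analysis for non-ignorable missingness.

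Protocol section 14 gives the post-training scan as one hour and places the RAVLT, oral trail-making and FAS word fluency at the start of that visit.

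**The concern.** The scan is the only source of the primary outcome, and the sequence gives it up at the first fallback. A drop-out who would come in for a scan, but not for the scan and both cognitive sessions, is next asked for something that cannot yield FC. That value is then missing because of the order of the offers, not because a scan was refused.

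An intention-to-treat analysis depends on outcomes from people who stopped training. Section 17 expects exercise effects to follow a dose-response pattern, so drop-outs may well differ from completers in their FC change. It also accepts that nobody can establish whether the missingness is ignorable. Observed scans in drop-outs are the best protection against that uncertainty.

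**Working it through.** **Offers set against the primary outcome**

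- Offer 1, MRI plus full cognitive testing: yields FC.
- Offer 2, one 2-hour cognitive session: learning and memory measures and the short battery, no FC.
- Offer 3, phone survey: no FC.
- MRI visit without the full cognitive set: not offered. SAP section 17 has no text on post-testing of drop-outs.

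**Burden, from the protocol's own times**

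- Offer 1: 1 h scan (section 14) + 2 × 2 h cognitive sessions (section 12) = 5 h, plus the short tests before the scan.
- MRI visit alone: 1 h of scanning plus those short tests, whose length is not given. It therefore takes more than 1 h.
- Resting-state acquisition within it: 3 × 8 = 24 min.

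**The plan's power figure**

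Inputs from section 17: 60 per group, 95% power at N = 120, about 90% two-tailed at about N = 100 after roughly 15% (18) missing. From section 13: 10% drop-out (12) and 5% motion (6), so 120 − 18 = 102. Alpha and the effect size are not stated. I assume two-sided 0.05 and solve for the effect:

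- d = (1.960 + 1.645) × √(2/60) = 0.658
- Power(N) = Φ(d × √(N/4) − 1.960)
- N = 100: Φ(3.291 − 1.960) = Φ(1.331) = 90.8%
- N = 102: Φ(3.324 − 1.960) = Φ(1.364) = 91.4%

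A noncentral F calculation with 10 predictors and a 1-df test gives 90.7% at N = 100. The plan's figure is reproduced, given its own 95% as an input.

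**What a scan offer could recover**

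Let s be the share of the 12 planned drop-outs who would accept a scan but not everything. The documents do not give s, so the full range is shown. With 5% of recovered scans lost to motion, N = 102 + 12 × s × 0.95:

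| s | Scans recovered | N | Power |
|---|---|---|---|
| 0 | 0 | 102 | 91.4% |
| 25% | 2.85 | 104.8 | 92.1% |
| 50% | 5.7 | 107.7 | 92.7% |
| 100% | 11.4 | 113.4 | 93.9% |

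Section 13 allows up to 6 non-randomized partners. If they come on top of the 18, the base is 96 and power runs from 89.7% (s = 0) to 92.7% (s = 100%, N = 107.4).

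The gain is therefore 0 to about 3 points. Two limits apply. The back-solved effect comes from a power analysis on learning rate, not FC. The calculation also counts every recovered scan as a usable 6-month value, so it is an upper bound.

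**The case against.** **Timing.** Section 13 places this testing at drop-out, while the primary outcome is FC at the end of the 6-month trial. A scan taken a few weeks into training is not that outcome. This stands, and it shapes the fix. It applies equally to the scan that offer 1 already seeks.

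**Learning matters too.** Section 17 bases the power analysis on learning rate because of its importance to the objectives, and its adherence paragraphs name FC and learning together as primary outcomes. Section 13 also states its reason for the cognitive session. Ranking the scan strictly above that session would be a trade-off, not the correction of a slip. This stands, but it is no argument against offering the scan as well.

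**Planned safeguards.** The pattern-mixture analysis is aimed at drop-outs who respond differently, and the imputation model, which is not specified, could use baseline FC and fallback cognitive scores. This mitigates the loss. It does not supply observed outcomes.

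**Stronger readings a reader might infer**

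- *The protocol contradicts itself*, because section 14 says "we will prioritize T1 structural images and resting state fMRI scans which are central to testing our specific aims". That rule concerns people uncomfortable in the scanner and ranks sequences within a scan. It does not rank MRI against cognitive testing.
- *The treatment effect will be overstated by a known amount.* If completers have effect d and the 10% who drop out have none, the true effect is 0.90d. Imputing drop-outs entirely from completers gives d, and 1/0.90 = 1.11. Scanning 6 of 12 gives 108/114 = 0.947d, and 0.947/0.90 = 1.05. The documents support neither the zero effect, nor the share accepting, nor imputation from completers only, nor treating an early scan as the 6-month value. Even on those terms the shift is 0.053d, or 0.053 × 0.658 = 0.035 SD, against a standard error of √(4/102) = 0.198 SD.
- *Twelve outcomes will be lost.* Some drop-outs may accept offer 1, others may refuse any scan, and section 13 itself now expects smaller losses than first planned.

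**Conclusion.** The gap is real and modest. As written, the sequence can lose FC in drop-outs who would have accepted a scan without the full cognitive set, and nothing in the SAP repairs this. The number affected is unknown and, on the plan's own allowance, at most 12 of 120. Power is a minor matter. The main cost is that the primary outcome goes missing selectively in the people whose response is least certain, leaving more of the intention-to-treat estimate to untestable assumptions. Neither the direction nor the size of any bias can be derived from the documents. This is a cheap improvement worth making, not a flaw that invalidates the primary analysis.

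**What to change.** In protocol section 13, after the full-set offer and before settling for cognitive testing only, add an offer of the post-test MRI visit. It should cover at least T1 and resting state, with the RAVLT, oral trail-making and FAS already attached to that visit. Make this offer alongside the one 2-hour cognitive session, and take both where the person can give both. The phone survey stays last.

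Ask for the scan at the scheduled 6-month time where the person is willing, otherwise at drop-out. Record the scan date relative to the planned last visit, and the reason for each missing scan by arm. State in SAP section 17 how off-schedule scans are used. An early scan can inform the imputation and sensitivity analyses, but should not enter the primary model as the 6-month value without saying so.

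The cost is a short protocol edit, a revised script for coordinators and a sentence or two in the SAP. Scanner time for off-schedule visits would have to be arranged, as the documents do not say how that would be covered. A few drop-outs who will give only one visit may provide the scan and short battery instead of the learning tasks, which is a genuine loss for the learning analyses.

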Following the acute exercise session, participants will continue to the second phase by entering one of two training groups, as determined by their initial randomization:

- **Moderate intensity exercise training** will be a 24-week supervised cycling program, with supervision directly from our research team. Participants will start in waves of ~5 per wave. All participants will first receive a one-on-one orientation with an exercise training specialist that has been trained by [name] in monitoring an exercise program for healthy older adults. Since participants will initially be relatively inactive, the exercise group will start with a 5 minute-warm-up, 20-minutes moderate intensity cycling at 50-60% Heart Rate Reserve (HHR) and 20 minutes passive cycling, and 5 minute cool-down per session, for 3 sessions/week. In each additional week, we will replace 5 minutes of passive cycling with 5 minutes of moderate intensity cycling per session, until the total time for moderate intensity is 40 minutes per session by the start of week 5 (with additional 5 minute warm-up and 5 minute cool-down). Starting at week 6 the exercise group will increase their moderate intensity cycling to 60-70% HHR with a similar build up to the first 5 weeks. Starting at week 13 the exercise group will increase their moderate intensity cycling to 70-80% HHR with a similar build up to the first 5 weeks. This program allows for a gradual build-up of endurance while including training for approximately 135 minutes of moderate-to-vigorous intensity exercise per week.
- **Functional fitness training** will be a 24-week supervised exercise program designed to focus on functional flexibility and mobility, with supervision directly from our research team. All participants will first receive a one-on-one orientation with an exercise training specialist that has been trained by [name] in monitoring an exercise program for healthy older adults. Training will start with a 15 minute-warm-up of stretching, 20 minutes of light intensity cycling and 15 minutes of dynamic stretching to increase range of motion and functional fitness, for 3 sessions/week. In each additional week, additional stretches will be added to maintain variety and improve flexibility of all major muscle groups. Our goal is to maintain HR at or below 40% HRR during training sessions for this group.

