Both groups will wear a Heart Rate Monitor (Polar wrist watch and chest-band) during their exercise sessions. We will download HR monitor data following each session and this data will be used to give feedback on their target HR for the following session. Target HR for each condition will be based on the baseline maximal exercise test. Ratings of perceived exertion (RPE) will also be collected during the baseline max test, and in cases where there was a discrepancy between expected RPE and HR during this test, RPE will be used in conjunction with HR in developing a target HR for moderate and passive cycling sessions.

All training sessions in the first two weeks are scheduled to be in our lab. After the first two weeks, participants can do up to two sessions per week outside the lab. At the conclusion of each training session in the lab, participants are given instructions on how to complete their training at home including use of the HR monitor. In order to maintain blinding to intensity prescriptions, participants are guided to mimic the heart rate zones they are targeting in their lab sessions. For participants that live outside of a 30-mile radius, we have an additional option for more frequent home training sessions, provided that participants demonstrate they can charge and upload their HR data to Polar Flow (online) for trainer review and feedback at least once per week.

16. General Data Management/Quality Assurance

Paper/hard copy records (hard copy surveys, questionnaires, case report forms, pictures, etc.)

- Standardized procedures will be used to collect and maintain basic demographic and health data on all participants, including: (1) collecting names, email addresses, and phone numbers; (2) contacting participants with personalized letters and cards via email; (3) maintaining phone contact with participants throughout the study; (4) setting up a (secure and access-restricted) tracking file with names, email addresses, phone numbers, projected session times.
- All contact information will be stored on a secure file server and will be kept separate from study data. Once a participant has been contacted and screened with our screening session, and qualifies for the study, they will be assigned a subject number and all testing materials beyond that point will contain only the subject number.

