Therefore, in a series of un-blinded exploratory per-protocol analyses (27), we will test the extent to which adherence and training context affects training-induced change in primary outcomes of hippocampal-cortical FC and learning. Based on the issues outlined above, analyses will initially be based on pre-planned definitions of context and adherence. First, we will test the extent to which training heart rate (HR) differed in the lab compared to home sessions as a function of intervention group. Based on preliminary descriptive data, we predict that HR will be higher during home sessions for both groups, but there will be no average group differences in this context effect. Second, we will test all training group effects described above with an additional continuous interaction term for %sessions completed. We predict that greater sessions attended will have a weak to moderate effect on the benefit of M compared to L intensity training. Third, we will test the same group interactions with a continuous interaction term for %sessions in the prescribed HR zone. We predict this will have a moderate to strong effect on primary outcomes, as adhering to the intensity prescription is predicted to have a stronger effect than attendance alone. A final analysis will further unpack the direction of intensity adherence, with negative values indicating the percent of sessions below the prescribed HR zone and positive values indicating the percent of sessions above the prescribed HR zone. This final intensity adherence analysis will test both *whether* and *how* gains in benefits were associated with variations in adherence to prescribed HR intensity.

18. Safety

There are no known risks to participating in the questionnaire assessments or cognitive tests. There may be risks involved in exercising on a motorized bicycle: participants may become fatigued or uncomfortable while exercising. Additionally, there may be a small risk of loss of confidentiality associated with study participation. Listed below are potential risks associated with assessments to be completed throughout the trial:

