Therefore, in a series of un-blinded exploratory per-protocol analyses (4), we will test the extent to which adherence and training context affects training-induced change in primary outcomes of hippocampal-cortical functional connectivity and learning. Based on the issues outlined above, analyses will initially be based on pre-planned definitions of context and adherence. First, we will test the extent to which training HR differed in the lab compared to home sessions as a function of intervention group. Based on preliminary descriptive data, we predict that HR will be higher at home sessions for both groups, but there will be no average group differences in this context effect. Second, we will test all group interactions described above with an additional continuous interaction term for %sessions completed. We predict that greater sessions attended will have a weak to moderate effect on benefit of M compared to L intensity training. Third, we will test the same group interactions with a continuous interaction term for %sessions in the prescribed HR zone. We predict this will have a moderate to strong effect on primary outcomes, as adhering to the intensity prescription is predicted to have a stronger effect than attendance alone. A final analysis will further unpack the direction of intensity adherence, with negative values indicating the percent of sessions below the prescribed HR zone and positive values indicating the percent of sessions above the prescribed HR zone. This final intensity adherence analysis will test both *whether* and *how* gains in benefits were associated with variations in adherence to prescribed HR intensity.

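### The exploratory lab-versus-home heart-rate comparison is confounded with the moderate arm's intensity steps, by an amount and in a direction that depend on when home sessions are used

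*Protocol*

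**What the plan says.** Under the adherence and training context paragraphs of Protocol Section 17, the first planned analysis asks how far "training heart rate (HR) differed in the lab compared to home sessions as a function of intervention group". The SAP repeats it: "we will test the extent to which training HR differed in the lab compared to home sessions as a function of intervention group". Both expect heart rate to be higher at home in both arms. The Protocol adds that "there will be no average group differences in this context effect". The series is described as "in a series of un-blinded exploratory per-protocol analyses". Neither document gives a model for this test or names a term for week, training phase or prescribed zone.

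Protocol Section 15 fixes where and how hard participants train:

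- Location: "All training sessions in the first two weeks are scheduled to be in our lab". Then: "After the first two weeks, participants can do up to two sessions per week outside the lab". Participants living more than 30 miles away may do more at home.
- Moderate arm: 50-60% HRR at the start. "Starting at week 6 the exercise group will increase their moderate intensity cycling to 60-70% HHR" (the Protocol's HHR is heart rate reserve). From week 13 the zone is 70-80%.
- Light arm: at or below 40% HRR for the whole 24 weeks.
- Target heart rates are based on the baseline maximal test, so the moderate arm's prescribed heart rate rises with each step.

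**The concern.** Location and prescribed intensity are linked by the schedule, and in one arm only. The moderate arm's first six sessions are all in the lab and all in the lowest zone, and the later, harder weeks may mix lab and home. The light arm has a single ceiling, so its location mix makes no difference to what is prescribed. A comparison of training heart rate by location and group therefore picks up the escalation schedule as well as any effect of setting.

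Two wrong conclusions are possible. The trial could report that home training changed the dose differently in the two arms when every participant did as prescribed. Or a real problem could be hidden. Section 17 itself raises the possibility that light-arm participants exceed their zone at home. If they did so by about 3 points of HRR while the moderate arm had a +3.0-point artefact and no true context effect, the two would cancel. Both stated predictions would then appear confirmed.

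**Working it through.** The documents give no figure for the lab-home contrast, so there is none to reproduce. The check sets the true context effect to zero, assumes perfect adherence, and asks what difference the schedule alone produces.

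**Inputs (Protocol Section 15).** Three sessions a week for 24 weeks. Moderate-arm zone midpoints z: 55 in weeks 1-5, 65 in weeks 6-12, 75 in weeks 13-24 (% HRR). Home sessions in week w: h = 0 in weeks 1-2 and, as a rule, 0 to 2 from week 3. The light arm is taken as flat, so its lab-home difference is 0 for any pattern.

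**Formula.** Artefact = Σ(h·z)/Σh − Σ((3−h)·z)/Σ(3−h), summed over the 24 weeks. The total of z over all 72 sessions is 3 × (5×55 + 7×65 + 12×75) = 4890.

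**Two home sessions a week from week 3** (the normal maximum):

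- Home: 22 × 2 = 44 sessions; (6×55 + 14×65 + 24×75)/44 = 3040/44 = 69.1.
- Lab: 72 − 44 = 28 sessions; (4890 − 3040)/28 = 1850/28 = 66.1.
- Artefact: +3.0 points of HRR.

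**Other patterns.** The documents do not fix home use, so these are assumed. Changes are linear from week 3 to week 24.

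| Home sessions per week | Home mean | Lab mean | Artefact, all weeks | Artefact, weeks 3-24 only |
|---|---|---|---|---|
| 2, constant | 69.1 | 66.1 | +3.0 | 0.0 |
| 1, constant | 69.1 | 67.4 | +1.7 | 0.0 |
| 0.5 rising to 2 | 71.4 | 65.8 | +5.6 | +3.9 |
| 2 falling to 1 | 67.8 | 68.0 | −0.2 | −2.6 |
| 2 falling to 0.5 | 66.8 | 68.6 | −1.8 | −3.9 |
| 2 in weeks 3-12, then none | 62.0 | 70.2 | −8.2 | −10.2 |
| 3, constant (possible for distant participants) | 69.1 | 55.0 | +14.1 | no lab sessions |

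The last two columns show that dropping weeks 1-2 removes the artefact only when home use is constant. When use drifts, a difference remains, and for 2 falling to 1 it grows from −0.2 to −2.6.

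**If heart rate is averaged over all 40 cycling minutes**, the early passive minutes lower the lab mean further. With passive cycling assumed at 20-40% HRR, the figure at two home sessions a week is +3.6 to +5.9, depending on how the build-up in the later blocks is read.

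**In beats per minute.** The documents give no heart rate reserve. For an assumed 60 to 100 bpm, 3.0 points is 1.8 to 3.0 bpm.

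**Effect on the test.** This also needs the SD of the person-level home-minus-lab difference, which the documents do not give. Illustration: reserve 80 bpm, 50 per arm (about 100 analysable, Section 17), two-sided 5% test, SE = SD × √(2/50) = 0.2 × SD.

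- Two home sessions a week (2.42 bpm): SD 5 gives 2.42/1.0 = 2.42 standard errors and about 68% false rejection; SD 10 gives 1.21 and about 23%.
- One home session a week (1.35 bpm): SD 5 gives about 27%; SD 10 about 10%.

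**After the fix.** With perfect adherence, heart rate minus that session's target is the same in lab and home sessions, so the artefact is 0 in every pattern. Within a single week or zone block z is constant, so a lab-home comparison there also gives 0.

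**The case against.** The plan gives one sentence and no model. It speaks of pre-planned definitions of context and adherence, and a session-level model with week or target would be compatible with the text. That is fair: the test is under-specified rather than stated as an unadjusted comparison. But neither document supplies a definition or an adjustment for this test, and the contrast as worded mixes setting with dose.

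The analysis is also exploratory, has heart rate as its outcome, and feeds no intention-to-treat result. The same section goes on to analyse the percentage of sessions in the prescribed zone, and then the percentage below and above it. Those measures are relative to the prescription, so the steps do not bias them in this way. This limits the consequence. They are not split by location, however, so they do not answer the lab-home question.

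A reader might infer that the moderate arm must show higher heart rate at home. The documents do not support that: they set a usual upper limit on home sessions, not how they are spread over the weeks, and the sign reverses if use falls off steeply. A reader might also take high false-positive rates as established. They rest on an assumed reserve, SD and home pattern, and at one home session a week with a large SD the inflation is small.

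**Conclusion.** The point holds as a confounding problem in one exploratory analysis. Under perfect adherence and no context effect, the schedule alone can produce a lab-home difference in the moderate arm and none in the light arm. The size is about +3.0 points of HRR at a constant two home sessions a week and +1.7 at one. It is close to zero if use falls from two to one, and negative if it falls further. These figures rest on zone midpoints, the full zone step at weeks 6 and 13, and a flat light arm. The bpm and rejection figures rest in addition on values the documents do not give, and should be read as illustrations. The planned test could therefore suggest a group difference that is not there, or hide one that is.

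It would be wrong to infer that the primary connectivity comparison is biased, because it does not use this analysis. The change is worth making because it costs little and the question of dose at home matters for interpreting the trial.

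**What to change.** In the adherence and training context text of Protocol Section 17 and the SAP, state one of the following for the lab-home test:

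1. The outcome is each session's heart rate relative to that session's individual prescribed target or zone. For the light arm, subtracting its constant ceiling leaves the lab-home difference unchanged.
2. Lab and home are compared within training week or zone block, by including week or zone block by group in the session-level model.

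Either removes the artefact under perfect adherence. The second is safer if the shortfall from target grows in the higher zones, a difficulty Section 17 anticipates. Restricting the comparison to weeks 3-24 is not sufficient on its own and is not required.

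The cost is slightly more analysis work. Section 15 already has heart-rate data downloaded after lab sessions and uploaded from home; session date and location need to be linked to them. Nothing changes in the exercise prescription or trial conduct.
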